For the closed report, enrollment and eligibility violations will be summarized by treatment group.

5 Baseline Characteristics

Baseline characteristics will be based on information collected on baseline and screening forms. Separate summaries will be provided for the Aviptadil and Remdesivir analysis cohorts.

For the open report, data will be pooled across treatment groups. In addition to the overall summaries, selected baseline characteristics will also be summarized by disease severity at study entry (2 strata, by use of *invasive mechanical ventilation or ECMO*).

For the closed report, baseline characteristics will be summarized by treatment group. For interim closed reports, baseline characteristics will usually be summarized by **modified intention-to-treat (mITT)**, for consistency with the safety summaries.

Unless noted otherwise, categorical variables will be summarized with the number and percentage (N, %) of participants in each category, and continuous variables will be summarized with the median and interquartile range (IQR); in the open report, in addition, the mean (SD) and range may be provided.

The following baseline characteristics will be reported:

- Number of participants with baseline data, overall and by study design stratum (N, %)
- Demographics
 - Age: distribution in categories 18-39, 40-49, 50-59, 60-69, 70-79, ≥ 80 years; and summary as continuous variable
 - Sex at birth
 - Ethnic group: Asian, Black, Latino/Hispanic, White, other
 - Country of enrollment

- Type of residence prior to COVID-19 (“home”)
- COVID-19 related characteristics
 - Duration of symptoms prior to enrollment
 - Level of care: non-ICU versus ICU
 - Respiratory support (4 categories: high-flow nasal cannula [HFNC], non-invasive ventilation [NIV], invasive mechanical ventilation without ECMO, or ECMO)
 - Time since initiation of oxygen support
 - Extent of lung infiltrates (3 categories: none, unilateral, bilateral)
 - ARDS (defined as bilateral lung infiltrates and SF ratio <315)
 - Receipt of SARS-CoV-2 vaccination (N, %)
 - Fully vaccinated at the onset of COVID-19 symptoms (\geq 14 days after the final vaccine dose [\geq 14 days since second dose, or since first dose if only one dose is required])
 - Type of vaccine
 - Received as part of a blinded clinical trial
- Vital signs (median [IQR] and categories)
 - Respiratory rate (categories: \leq 20 vs $>$ 20 breaths/minute)
 - Oxygen saturation (SpO2) (categories: <92%, 92-96%, $>$ 96%)
 - Fraction of inspired oxygen (FiO2) (categories: <0.30, 0.31-0.40, 0.41-0.70, $>$ 0.70)
 - SpO2:FiO2 (SF ratio) (categories: <315, \geq 315)
 - Temperature (categories: $<$ 38° C, \geq 38° C)
 - Heart rate (categories: <100, \geq 100 bpm)
 - Systolic blood pressure (SBP) (categories: <90 mmHg, 90-110 mmHg, $>$ 110 mmHg)
 - Mean arterial pressure (MAP) (4 categories: <65 mmHg with vasopressor use, <65 mmHg without vasopressor use, \geq 65 mmHg with vasopressor use, \geq 65 mmHg without vasopressor use)
 - Current vasopressor use
 - ARDS: SF ratio < 315 and bilateral pulmonary infiltrates
- Acute organ dysfunction during the index COVID-19 illness
 - Cardiac and vascular dysfunction
 - Hematologic dysfunction
 - Hepatic decompensation (exclusion criterion for aviptadil)
 - Serious infection other than SARS-CoV-2 (respiratory and non-respiratory)
 - Neurologic dysfunction
 - Renal dysfunction
- History of chronic conditions (present prior to the index COVID-19 illness)
 - Compromised immune function, defined as current use of antirejection medication after transplant, cytotoxic chemotherapy, or treatment with biological medicine for autoimmune disease or cancer; HIV; or immunosuppressive disorder other than HIV.
 - Metabolic/vascular co-morbidities, defined as history of diabetes mellitus requiring treatment, a cerebrovascular event (thrombotic or hemorrhagic), heart failure, or an MI or other acute coronary syndrome, overall and by components
 - Hypertension with and without history of other metabolic and vascular co-morbidity (4 groups):
 - i) no hypertension or other metabolic/vascular co-morbidity;
 - ii) hypertension without metabolic/vascular co-morbidity;
 - iii) metabolic/vascular condition without hypertension; and
 - iv) hypertension and a metabolic/vascular co-morbidity.

- Metabolic/vascular co-morbidities include a history of diabetes, a cerebrovascular event, heart failure, or an MI or other acute coronary syndrome
 - Renal impairment or requirement of renal replacement therapy, overall and by components
 - Chronic obstructive pulmonary disease (COPD)
 - Chronic continuous supplemental oxygen use
 - Hepatic impairment
 - Cancer
- Other clinical characteristics
 - BMI (<30, 30-39.9, 40+)
 - Pregnancy, and gestational age (remdesivir cohort only, as pregnancy is an exclusion criterion for aviptadil)
- COVID-19 treatments
 - Receipt of remdesivir prior to randomization (N, %), and number of days
 - Corticosteroid use, summarized overall, and by disease severity at study entry (receipt of *invasive mechanical ventilation or ECMO*)
 - Antiplatelet/anticoagulant therapy (none; prophylactic heparin; intermediate or therapeutic heparin or other anticoagulant therapy; aspirin; or other antiplatelet therapy)
 - Immune modulators (IL-1 inhibitors, IL-6 inhibitors, interferons, JAK inhibitors, TNF inhibitors, other)
 - Convalescent plasma for SARS-CoV-2 infection
 - Hyperimmune intravenous immunoglobulin (hIVIG)
 - Neutralizing monoclonal antibodies for SARS-CoV-2
- Pulmonary vasodilators, by type
- Sedatives, by type
- Blood pressure lowering medications, by type
- Other concomitant medications
 - Antidiarrheals
 - Antifungals
 - Antirejection medications
 - Biologics for cancer or autoimmune disease
 - Cytotoxic chemotherapy
 - NSAIDs (at least 7 days)
- Laboratory values: as continuous outcomes, and number (%) of grade 3 or 4 lab abnormalities according to the *DAIDS AE Grading Table*.
- Co-enrollment in other trials, by trial
- Genomics consent

Some biomarkers will be measured centrally from stored samples, for example, SARS-CoV-2 antigen and antibody levels in plasma and SARS-CoV-2 viral RNA from nasal mid-turbinate swabs. If these measures are available, they will be included in interim reports.

Open report only:

In addition to the overall summaries, selected baseline characteristics will also be summarized by study design stratum, including age, gender, race/ethnicity, geographic region, disease severity, admission to ICU, duration of symptoms prior to enrollment, and duration of support for respiratory failure.

6 Administration of Study Treatment

These data are an important part of the safety review, with particular emphasis on infusion-related reactions and symptoms occurring during or within up to 2 hours after the infusion. These reactions and symptoms will be graded according to the DAIDS AE Grading Table.

The administration of study treatment is also an essential element of study conduct. The data summaries described in this section will be provided:

- In the closed report to the DSMB, by treatment group
- In the open report, selected summaries describing adherence, pooled across treatment groups

Summaries of AEs or infusion-related reactions are restricted to the closed report. Selected summaries will also be provided separately for the two disease severity strata.

Analyses will be by modified intention-to-treat (mITT), unless specified otherwise. The treatment comparisons will be performed using the methods described in section 3 for binary and continuous outcomes: stratified CMH test or logistic regression for comparing percentages, Wilcoxon rank-sum test [or quantile regression] for comparing medians, ANCOVA models for comparing means.

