Each randomization of investigational agent versus placebo will use a 1:1 allocation, and equal allocation to the four treatment combinations in the 2x2 factorial. Statistical analyses will compare aviptadil versus placebo, pooling participants in strata 1, 2, and 4, and will compare remdesivir versus placebo, pooling participants in strata 1 and 3. To achieve this, it is estimated that 800 participants will have to be enrolled (640 for each pairwise comparison: aviptadil vs. placebo, and remdesivir vs. placebo).

The design assumes that the effects of aviptadil and remdesivir are independent of each other; a possible interaction between the two investigational agents will be assessed in the 2x2 factorial, although power is limited for the interaction test.

Figure 1: Study Design of TESICO. The study includes 4 “design strata”: a 2x2 factorial for aviptadil (VIP) versus placebo and remdesivir versus placebo, and 3 strata with 1:1 randomizations to either investigational agent versus placebo.

Stratum	Percent of Patients
1	60
2	10
3	10
4	20
Sample size for VIP = strata 1, 2 and 4	
Sample size for R = strata 1 and 3	

Population

The study population consists of inpatient adults (≥ 18 years) who have documented SARS-CoV-2 infection within 14 days of enrollment and are receiving high-flow nasal cannula, non-invasive ventilation, invasive mechanical ventilation, or ECMO at enrollment, in whom the current respiratory failure is thought to be due to SARS-CoV-2 infection and in whom respiratory support was initiated within 4 days prior to randomization.

Additional eligibility criteria apply for aviptadil and remdesivir. Participants who have received remdesivir prior to study entry are excluded from randomization to remdesivir.

The **primary endpoint** is a 6-category ordinal outcome that assesses the recovery status of the patient at Day 90, described in [Appendix A](#), and is referred to as “**recovery**”. The categories of the ordinal outcome, from best to worst, start with 3 categories of “recovery” defined by the number of days alive at home and not on new supplemental oxygen, followed by 3 categories for “not recovered” defined as a) discharged but not to home or at home but still requiring continued new supplemental oxygen, b) hospitalized or receiving hospice care, and c) death at day 90.

Primary Objectives

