1.4 Sample Size Estimates

The sample size calculations are aimed at the pairwise comparisons between each of the two investigational agents and its matched placebo. A total sample size of 800 participants is estimated.

To address the first primary objective, participants who are randomized to aviptadil will be compared to those randomized to the matched aviptadil placebo, pooled over design strata 1,

2 and 4. For the second primary objective, participants who are randomized to remdesivir will be compared to those randomized to the matched remdesivir placebo, pooled over design strata 1 and 3. Treatment groups will be compared by intention-to-treat for the 6-category ordinal outcome of recovery on Day 90 (primary outcome) using proportional odds models.

The planned sample size for each pairwise comparison is 640 participants (320 participants in each group, pooled across the corresponding design strata). The sample size is sufficient to detect an odds ratio (OR) of 1.5 with 80% power, using a two-sided test with a significance level of 0.05.

Participants in design stratum 1 (2x2 factorial) will contribute to both comparisons; assuming that 60%, 10%, 10%, and 20% will be enrolled in trial design strata 1-4, respectively, 800 participants in total will result in 640 participants for each of the two pairwise comparisons. The total sample size, which depends on the percentage of participants enrolled in the factorial design, will be periodically assessed by the protocol team.

Sample size calculations are described in detail in Section 6.3 of the protocol.

Blinded sample size re-estimation will be carried out before enrollment is complete to determine whether the planned sample size of 640 participants for each of the pairwise comparisons, followed for 90 days, will be sufficient to adequately power the trial. The blinded sample size re-estimation does not involve unblinding of the treatment difference. It will be based on the pooled outcome data, the relative enrollment into the two disease strata and four design strata, the number of withdrawals prior to the infusion, adherence to the blinded infusions, and the amount of missing data.

2 Interim DSMB Reviews: Goals and Format

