Each investigational agent versus control will be reviewed as a separate clinical trial. For full DSMB reviews, a joint open report will be provided for aviptadil and remdesivir, with separate data summaries for the aviptadil and remdesivir cohorts (defined below), and key summaries by the four design strata. Separate closed reports will be provided for aviptadil and remdesivir, with similar layouts of the data summaries.

Analysis cohorts: Safety and efficacy analyses (closed reports) will be conducted for the Aviptadil and Remdesivir cohorts, and the Factorial cohort will be used to assess whether the effects of aviptadil and remdesivir are independent:

1. **Aviptadil cohort:** Participants who were randomized to aviptadil or its placebo (design strata 1, 2, and 4)
2. **Remdesivir cohort:** Participants who were randomized to remdesivir or its placebo (design strata 1 and 3)
3. **Factorial cohort:** Participants who were randomized to the four treatment combinations formed by the aviptadil/placebo and remdesivir/placebo pairs (2x2 factorial design; design stratum 1).

For the factorial cohort, analyses will focus on assessing whether the effects of aviptadil and remdesivir are independent of each other, described in section 9.

Goals of the interim reviews:

- Protect the safety of study participants.
- Advise on stopping or modifying the trial for patient safety in case of emerging data on harm, or for efficacy in case of evidence of overwhelming benefit.
- After the first 40 participants are enrolled for the aviptadil vs placebo comparison, review safety and study implementation
- Review the conduct of the trial

Timing of the reviews: The DSMB will conduct frequent safety reviews. The initial safety review for either investigational agent will be conducted after approximately 40 participants are enrolled and have Day 5 data available, or earlier. Subsequent full reviews will be timed according to the recommendations of the DSMB and study leadership.

After the initial safety review, weekly safety reports for aviptadil versus placebo will be provided to the DSMB. At the discretion of the DSMB, the frequency of these (initially weekly) safety reports may be modified. ***The DSMB may request interim reports that are focused on safety at any time.***

Review meetings will typically consist of an Executive session (optional; closed), open session, closed session, and a second open session to give feedback to study leadership (optional).

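### At the stated stratum mix, 800 participants give 720 for aviptadil and 560 for remdesivir, not 640 each, so remdesivir falls below its stated 80% power at that total

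*SAP*

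**What the plan says.** SAP section 1.4 gives the total: "A total sample size of 800 participants is estimated". It then gives the target for each agent: "The planned sample size for each pairwise comparison is 640 participants (320 participants in each group, pooled across the corresponding design strata"). Power is attached to that target: "The sample size is sufficient to detect an odds ratio (OR) of 1.5 with 80% power", at a two-sided 5% level. The link between the total and the two targets is the assumed mix across design strata: "60%, 10%, 10%, and 20% will be enrolled in trial design strata 1-4, respectively, 800 participants in total will result in 640 participants" for each comparison.

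Section 1.2 repeats the result: "it is estimated that 800 participants will have to be enrolled (640 for each pairwise comparison: aviptadil vs. placebo, and remdesivir vs. placebo"). Its Figure 1 table lists the same shares for strata 1 to 4 (60, 10, 10 and 20) and names the strata that count for each agent, including "Sample size for R = strata 1 and 3".

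Cohort membership is the same wherever it is defined (sections 1.2, 1.3, 1.4, 2 and 3): aviptadil is strata 1, 2 and 4; remdesivir is strata 1 and 3.

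Section 1.4 also says that the protocol team will review the total from time to time, and that a blinded re-estimation will take account of enrolment by design stratum.

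**The concern.** Two cohorts that share stratum 1 can be equal in size only if stratum 3 is as large as strata 2 and 4 together. Under the stated mix these are 10% and 30%, so the cohorts cannot both be 640 at any total.

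Remdesivir versus placebo is one of the two primary objectives, and the SAP treats each agent's comparison as a separate trial. The sentence in section 1.4 is what turns the 640 needed for each comparison into a total of 800. If it is wrong, a trial that enrols 800 exactly as assumed misses its own target for one primary objective and exceeds it for the other.

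**Working it through.** **Inputs, all from SAP sections 1.2 to 1.4 and 2:** total 800; shares 60%, 10%, 10% and 20% for strata 1 to 4 (sum 100%); aviptadil = strata 1 + 2 + 4; remdesivir = strata 1 + 3; 1:1 allocation; 640 per comparison for odds ratio 1.5, 80% power, two-sided 5%.

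**1. Is 640 itself reasonable?** The usual proportional-odds formula for the total in two equal groups is

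N = 12 (z₀.₉₇₅ + z₀.₈₀)² / [(ln OR)² (1 − Σp³)],

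where p are the category proportions averaged over the two groups. With 1.960 + 0.8416 = 2.8016 and ln 1.5 = 0.4055, N = 572.9 / (1 − Σp³). A total of 640 therefore implies 1 − Σp³ = 572.9/640 = 0.895. Six equal categories give the maximum, 1 − 6 × (1/6)³ = 0.972. So 640 is plausible, and the problem lies elsewhere.

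**2. Cohort sizes at 800**

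| Comparison | Share | Participants | Per group | Against 640 |
|---|---|---|---|---|
| Aviptadil | 60 + 10 + 20 = 90% | 720 | 360 | +80 (+12.5%) |
| Remdesivir | 60 + 10 = 70% | 560 | 280 | −80 (−12.5%) |

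The stated 640 is reproduced for neither agent. It is the average of the two: (720 + 560)/2 = 640.

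**3. Could the percentages be in the wrong order?** Of all the distinct orderings of 60, 10, 10 and 20 over the four strata, only 60/10/20/10 gives 640 for both: 60 + 10 + 10 = 80% for aviptadil and 60 + 20 = 80% for remdesivir. That is the stated mix with strata 3 and 4 exchanged.

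**4. Power at the sizes that the stated mix gives.** Taking 640 as exactly 80%, power at n is Φ(2.8016 × √(n/640) − 1.960).

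- Remdesivir, n = 560: Φ(2.8016 × 0.9354 − 1.960) = Φ(0.661) = 74.6%.
- Aviptadil, n = 720: Φ(2.8016 × 1.0607 − 1.960) = Φ(1.012) = 84.4%.
- Odds ratio detectable with 80% power at 560: exp(0.4055 × √(640/560)) = 1.54.

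**5. Range.** The assumed category proportions are not in the SAP, which refers to protocol section 6.3 for the detail; that section was not available for this check. In the most favourable case (1 − Σp³ = 0.972) the smallest total for 80% power is 572.9/0.972 ≈ 590, and power at 560 is 78.0%. So by this formula 560 is below 80% for every six-category distribution. If 640 gives at least 80%, as the SAP says, power at 560 lies between 74.6% and 78.0%. An assumed 1 − Σp³ of 0.85 would give 72.4%, but 640 would then give only 77.9%.

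**6. Total needed at the stated mix.** Remdesivir reaches 640 at 640/0.70 = 914.3, so about 915. Aviptadil reaches it at 640/0.90 = 711.1, so about 712.

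**The case against.** The best reply is that no loss of power has been shown. The SAP attaches 80% to 640 per comparison, not to 800 in total, and 640 is plausible. Power falls only if the stated percentages are the intended ones and enrolment stops at 800 with that mix. A clerical exchange of strata 3 and 4 explains the discrepancy exactly and would leave 800, 640 and 80% intact. The agreement of the Figure 1 table with section 1.4 is weak evidence against this, because a transposed pair would be copied into both. Section 8.5 shows a similar confusion: it sets stratum 1 against stratum 4 in the remdesivir subgroup analysis, although stratum 4 is randomised to aviptadil or placebo only.

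There are also safeguards. The 800 is called an estimate, blinded re-estimation considers the four design strata, and section 4 reports enrolment by stratum and for each comparison. A shortfall would be visible.

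Most of this stands. It makes the power loss conditional, and it means that the SAP does not reveal which figure is wrong. It does not reconcile the figures: 70% of 800 is not 640 under any reading. Nor is the periodic review fully protective as described. Section 1.4 ties the total to the share enrolled in the factorial part, yet with exactly 60% in stratum 1 that check would look on target while remdesivir stood at 560. The split between stratum 3 and strata 2 and 4 causes the imbalance.

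**Conclusion.** The concern holds. The percentages, the total of 800 and the 640 per comparison cannot all be right. Taken as written, the plan yields 720 for aviptadil and 560 for remdesivir. At 800 the remdesivir comparison then has about 75% power for an odds ratio of 1.5, or 2.0 to 5.4 points below 80% over the range 74.6% to 78.0%. Aviptadil has about 84%.

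The cohort sizes are exact. The 74.6% and 84.4% assume that 640 gives exactly 80%; the 78.0% is the upper bound by the standard formula. None of these allows for adjustment for disease severity or for missing outcomes. The shortfall would arise only if enrolment ended at 800 with the stated mix, and further enrolment could repair it. No analysis method is affected.

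**What to change.** First establish, from protocol section 6.3 and the planning records, which figures were intended. Then make one of two corrections in SAP section 1.2 (text and Figure 1 table) and section 1.4:

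- **If strata 3 and 4 were exchanged by mistake:** correct the two percentages in both places. The 800, the 640 and the 80% then stand.
- **If 60/10/10/20 is intended:** state that 800 yields 720 for aviptadil and 560 for remdesivir. Restate remdesivir power for an odds ratio of 1.5 as about 75% (80% for about 1.54), recalculated with the protocol's category proportions. Give about 915 as the total at which both comparisons reach at least 640.

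In either case, say that the total depends on the shares of all four strata and not only on the factorial share, and start the blinded re-estimation from the corrected figures. Because section 1.2 is adapted from the protocol, check the matching protocol text too.

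The cost is wording, and in the second case one less favourable power figure. Restating the figures needs no extra participants. Keeping 640 for remdesivir at the stated mix would need about 115 more (915 − 800), which is a separate decision for the re-estimation.

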6.1 Infusion of Aviptadil (Active or Placebo)

Study population (Aviptadil cohort, mITT): Unless otherwise noted, the study population consists of participants who were randomized to aviptadil or its placebo, excluding those who did not receive **any** aviptadil/placebo (modified intention-to-treat [mITT]).

Aviptadil (and its placebo) will be administered by intravenous infusion for 3 days, over a continuous 12 hour period each day. The protocol-specified infusion rate for the first infusion day is 50 pmol/kg/hr (Day 0), to be increased to 100 pmol/kg/hr on Day 1 and 150 pmol/kg/hr on Day 2. This corresponds to a protocol-specified dose of 600, 1200, or 1800 pmol/kg for infusions on Days 0-2. Infusions may be paused or discontinued due to side effects, or the target dose may be decreased.

In the following, “aviptadil” refers to the blinded aviptadil infusion (active or placebo). “Peri-infusion” refers to the time period during or within 2 hours after the infusion.

The following statistics will be used to summarize the infusions in each treatment group (active and placebo) for the closed reports, or pooled across treatment groups for open reports shared with investigators. For the closed report, treatment groups will be compared for the various outcomes using methods described in section 3.

For all participants who were randomized (**Aviptadil ITT cohort**):

- Non-administration of aviptadil:
Number and percentage of participants who did not receive any aviptadil, and reasons

All other analyses will use the **Aviptadil mITT** cohort (i.e., analyses will exclude those who did not receive any blinded aviptadil in the study).

- For each of the Days 0-2: number and percentage of participants who did not receive any aviptadil, and reasons
- Adherence to the study treatment on Days 0-2 will be summarized over time: percent of participants who received no infusion, some (<50% of the day's protocol-specified infusion dose), most (50-90%) and full infusion (>90%) for each of the three days, and overall.
 - For each day, for each participant, the "percent dose infused" will be the estimated dose delivered expressed as percentage of the protocol-specified dose for the day (600, 1200, or 1800 pmol/kg).
 - For the summary across Days 0-2 ("overall"), categories are formed by the average of the three daily percent doses infused.
- Day of first infusion (same day as randomization, next day, or > 1 day after randomization), and time between randomization and start of infusion (median hours, IQR).
- For each of the Days 0-2: **Infusion of aviptadil**, rate, dose, and infusion time
 - Pre-infusion summary:
 - starting (patient-specific planned) infusion rate (categories: at versus below the protocol-specified rate for the day)
 - blood pressure (MAP, SBP)
 - use of vasopressors and dose
 - receipt of antidiarrheal agents to prevent infusion reactions
 - Dose infused (as percent of goal): median, 25th and 75th percentile, and according to categories (full [>90% of goal]; most [50-90%]; some [<50%]; no infusion)
 - For participants who received an incomplete infusion of the study drug on any day, reasons for the incomplete infusion (all that apply)
 - Timing of administration
 - Duration of infusion: median, 25th and 75th percentile of infusion time
 - Infusion start times (8am-12:00 noon; 12:01pm- 6:00pm, > 6pm)
 - Decrease in the infusion rate during the day (overall: worst category across Days 0-2; and worst category by day) (closed report only):
 - No decrease
 - Flow rate decreased, but no intermittent stop. The reasons for the decrease will be summarized (due to AE versus other reasons)
 - Infusion was paused (stopped but resumed), and not discontinued prematurely for the day; and reasons (AE versus other)
 - Premature discontinuation for the day (infusion duration <12 hours, and patient-specific planned dose not delivered), and reasons for discontinuation (AE or other)
 - Permanent discontinuation, and reasons
 - Listings of participants for whom the infusion was discontinued early, with reason for discontinuation, dose infused per day, disease severity at baseline, age, sex.
 - Concomitant medications peri-infusion (i.e., during or within 2 hours after the infusion) (overall: any use peri-infusion on Days 0-2; and by day)
 - Vasopressors, with dose in norepinephrine equivalent (NE)
 - IV bolus or colloids
 - Other medications to treat AEs, as collected on the infusion eCRF

Safety: infusion-related signs/symptoms, AEs, and lab markers (closed report only)

The primary safety outcome of *grade 3 or 4 AEs, SAEs, PSESEs, or death through Day 5* includes potentially infusion-related outcomes; the analysis of the primary safety outcome is described in section 7. The current section describes safety analyses that are focused on the peri-infusion time period (i.e., during and within 2 hours after the infusion).

Peri-infusion signs and symptoms are reported as AEs (with grade and action taken) on eCRFs. Local labs are reported at baseline, Days 1 and 2 for all participants, and Days 3 and 5 if clinically available. Labs on Day 5 are reported for participants who are treated in the ICU.

Side effects of aviptadil observed in previous studies include:

- Hypotension with and without vasopressor
- Diarrhea
- Facial flushing
- Bradycardia
- Tachycardia

For the aviptadil versus placebo comparisons, incidence and management of hypotension in particular will be monitored in detail. Blood pressure is recorded prior to the start of the infusion and every 2 hours peri-infusion on each infusion day. Vasopressor use and dose are reported: prior to the start of the infusion, the highest dose peri-infusion, and the dose at 2 hours after the infusion.

The following data summaries will be provided overall for Days 0-2, and separately by day. Treatment groups will be compared using statistical methods described under “analysis principles” in section 3; comparisons will be stratified by disease severity at study entry (2 categories, by use of *invasive mechanical ventilation or ECMO*).

- Number and percentage of participants with infusion-related signs or symptoms (reported during the infusion or within 2 hours after the infusion), by type and grade, by type and grade cut-off (i.e., \geq grade 2, \geq grade 3, etc.), and by type and action taken.

Comments:

1. For aviptadil, **diarrhea is not included in the composite safety outcome** of incident grade 3 or 4 AEs, SAEs, PSESEs or death unless it is a SAE or leads to discontinuation of the infusion (for the day, or permanent discontinuation). Therefore, peri-infusion diarrhea AEs will be summarized in two ways: (1) as reported, and (2) restricted to diarrhea AEs that lead to discontinuation of the investigational agent.
2. Hypotension, diarrhea, facial flushing, bradycardia, and tachycardia are collected as part of the infusion-related signs and symptoms, and will be summarized by type and grade, and by type and action taken in response to the AE, as described above.

- **Peri-infusion hypotension summary**

- Peri-infusion hypotension AEs reported on infusion eCRF (by grade: highest grade on Days 0-2, or highest grade on the day for the day-specific summaries)
- Blood pressure (across days 0-2, and on each day)

- MAP decrease by > 20 mmHg from daily pre-infusion baseline
- Lowest peri-infusion MAP (mean [SD] across participants)
- Incidence of MAP < 65 mmHg (compared to daily pre-infusion baseline)
- Percentage of peri-infusion BP data points with MAP <65 mmHg (mean [SD] of percentage across participants)
- Infusion modifications for hypotension (prevalence on ≥ 1 day)
 - Infusion not attempted for hypotension/vasopressor use
 - For those with any infusion modification, summary of the highest-intensity infusion modification (across Days 0-2, and for each day): Rate decreased but infusion not paused; infusion paused but resumed; infusion discontinued for the day; infusion discontinued permanently
- Vasopressor use peri-infusion
 - New peri-infusion vasopressor use on any day among patients not receiving vasopressors pre-infusion on Day 0 (Number in subgroup, N, %)
 - New or increased peri-infusion vasopressor use on any day among patients who received vasopressors pre-infusion on Day 0 (Number in subgroup, N, %)
 - Maximum peri-infusion vasopressor rate increase within a study day from pre-infusion to peak (in NE units; max over Days 0-2, then mean across patients; 0 NE is imputed for time points when no vasopressor is used. If the maximal peri-infusion vasopressor dose is lower than the pre-infusion dose, then 0 NE will be imputed).
 - Percent with vasopressor rate higher at 2 hours post infusion than pre-infusion
 - Incidence of vasopressor rate increase by > 0.03 mcg/kg/min NE units peri-infusion relative to daily pre-infusion baseline (N, %)
 - Incidence of peak (absolute) vasopressor rate of > 0.1 mcg/kg/min NE units
- IV fluid use peri-infusion in response to hypotension AE
 - IV fluid (crystalloid ≥ 500 mL or equivalent colloid volume) peri-infusion, prevalence
 - For those who received IV fluid or colloid: maximum IV fluid volume on one day (max across days for each participant, then mean across participants)
- Summary of *SBP and MAP trajectories*, from infusion start to 2 hours after infusion
 - Mean trajectories will be plotted by treatment group, and compared using longitudinal models.
 - For selected participants, *individual trajectories* for MAP and SBP will be plotted for each of the infusion days. In particular, individual trajectories will be plotted for participants who used vasopressors, who experienced peri-infusion hypotension (MAP < 65 mmHg or hypotension AE), or for whom the infusion flow rate was decreased, the infusion paused, or discontinued. These events will be marked on the individual trajectories. Thus, the individual trajectories serve as “line listings” for hypotension events.

- Heart rate:
 - Mean trajectories over time, similar to MAP
 - Percent of participants for whom the peri-infusion heart rate decreased to below 60 bpm at any time, stayed between 60-100 bpm at all times, or reached >100 bpm at any time.
- Medications (other than vasopressors) received in response to AEs during or within 2 hours after infusion, number and percentage of participants and type of medication
- Listings of participants who died or experienced grade 3 or 4 AEs, SAEs, or PSESEs are provided as part of the safety analyses described in section 7.

